**Tool Revision History:**

Version Number	Version Date	Summary of Revisions Made
1	30 March 2020	Original version
1	30 March 2020	IRB Clarification Request Edits
2	30 March 2020	Corrected version date
3	31 March 2020	IRB Requested Revisions
4	31 March 2020	Updated Section 14.2 Costs to the Participant
5	15 April 2020	Changed study to multi-center

## **Statement of Compliance**

This study will be conducted in accordance with the Code of Federal Regulations on the Protection of Human Subjects (45 CFR Part 46), 21 CFR Parts 50, 56, 312, and 812 as applicable, any other applicable US government research regulations, and institutional research policies and procedures. The International Conference on Harmonisation (“ICH”) Guideline for Good Clinical Practice (“GCP”) (sometimes referred to as “ICH-GCP” or “E6”) will be applied only to the extent that it is compatible with FDA and DHHS regulations. The Principal Investigator will assure that no deviation from, or changes to the protocol will take place without prior agreement from the sponsor and documented approval from the Institutional Review Board (IRB), except where necessary to eliminate an immediate hazard(s) to the trial participants. All personnel involved in the conduct of this study have completed Human Subjects Protection Training.

## List of Abbreviations

AE	Adverse Event/Adverse Experience
CFR	Code of Federal Regulations
CRF	Case Report Form
CSOC	Clinical Study Oversight Committee
DCC	Data Coordinating Center
DHHS	Department of Health and Human Services
DSMB	Data and Safety Monitoring Board
FFR	Federal Financial Report
FWA	Federalwide Assurance
GCP	Good Clinical Practice
HIPAA	Health Insurance Portability and Accountability Act
ICF	Informed Consent Form
ICH	International Conference on Harmonisation
IRB	Institutional Review Board
ISM	Independent Safety Monitor
MOP	Manual of Procedures
N	Number (typically refers to participants)
NIH	National Institutes of Health
OHRP	Office for Human Research Protections
OHSR	Office of Human Subjects Research
PI	Principal Investigator
QA	Quality Assurance
QC	Quality Control
SAE	Serious Adverse Event/Serious Adverse Experience
SOP	Standard Operating Procedure
US	United States
HBOT	Hyperbaric Oxygen Therapy
COVID-19	2019 Novel Coronavirus

CONFIDENTIAL

This material is the property of the NYU School of Medicine and Langone Medical Center. Do not disclose or use except as authorized in writing by the study sponsor  
Interventional Template Version: 11 January 2019

## Protocol Summary

Title	Open Label Multi-Center Study of Emergency Hyperbaric Oxygen for Respiratory Distress in Patients with COVID-19
Short Title	Hyperbaric Oxygen for COVID-19 Patients
Brief Summary	
This is a multi center prospective pilot cohort study to evaluate the safety and preliminary efficacy of hyperbaric oxygen therapy (HBOT) as an emergency investigational device for treating patients with respiratory distress due to a novel coronavirus disease, COVID-19. HBOT is a therapy that has been FDA approved for the treatment of decompression sickness, gas gangrene, late effects of radiation and others. HBOT is a medical intervention using a rigid chamber and compressed oxygen to treat hypoxia and modulate negative inflammatory responses. It has demonstrated a good safety profile and has been shown to blunt the damaging immune responses in animal models.
 
The mechanism of respiratory failure in COVID-19 is unknown but lung pathology demonstrates "edema, proteinaceous exudate, focal reactive hyperplasia of pneumocytes with patchy inflammatory cellular infiltration and multi nucleated giant cells. Fibroplastic plugs were also noted in airspaces." One potential mechanism is thought to be due to a cytokine storm from an overwhelming viral load. Hyperbaric Oxygen therapy has been shown to modulate the immune system in the laboratory rat model and is used to modulate the inflammatory response in reperfusion injury. We hypothesize that hyperbaric oxygen may be useful to modulate the immune response in COVID-19 infected patients and increase oxygenation. A recently non-peer reviewed study of hyperbaric oxygenation in Wuhan, China demonstrated that it was well-tolerated, safe with clinical improvement of oxygenation for all five patients that were enrolled.
 
In summary, HBOT treatment will be provided to patients as an adjunct to standard therapy for a cohort of 40 COVID19-positive patients with respiratory distress at NYU Winthrop Hospital. All patients prior to the clinical application of HBOT will be evaluated by the primary care team and hyperbaric physician. During the interim analysis of the first 10 patients and after the intervention portion of this study, a chart review will be performed to compare the outcomes of intervention patients versus age and gender matched control patients who received standard of care.

Phase	Emergency Investigational Device
Objectives	Determine Safety and Efficacy of Hyperbaric Oxygen as an adjunctive treatment for COVID 19 hospitalized patients
Methodology	This is a prospective interventional cohort study that will evaluate the risks and benefits of HBOT utilization for COVID-19 confirmed patients in the hospital setting.
Endpoint	Primary endpoint: Death Secondary endpoints: Need for invasive mechanical ventilation, reduction in days on a ventilator Safety endpoints: Incidence of adverse events (AE) and severe adverse events (SAE)
Study Duration	Approximately two months, but subject to change given the nature of the ongoing pandemic.
Participant Duration	Duration of inpatient hospitalization.
Intervention	Up to 5 hyperbaric oxygen treatments at 2.0 ATA for 90 minutes dependent on the ability of the patient to participate
Population	Patients greater than 18 years of age diagnosed with COVID19 and under respiratory distress.

CONFIDENTIAL

This material is the property of the NYU School of Medicine and Langone Medical Center. Do not disclose or use except as authorized in writing by the study sponsor

Eligibility Criteria	
Inclusion criteria:
 
 
1. Laboratory confirmed COVID-19 positive or a clear clinical diagnosis of COVID-19
 
2. SpO2 <93% after trial of non-rebreather with no less than 85% SpO2
 
3. At least 18 years of age
 
4. No absolute contraindication for Hyperbaric Oxygen
 
 
Exclusion criteria:
 
 
1. Pregnancy
 
2. Untreated Pneumothorax
 

Study Sites	
NYU Winthrop Hospital          NYU Langone School of Medicine          Northwell Hospital          Cleveland Clinic          Loma Linda          Jacobi/Einstein          University of Kentucky Hospital          Westchester Medical Center          Geisinger Commonwealth School of Medicine          Spectrum Health Hospital          University of Illinois at Urbana-Champaign

Number of participants	
40 patients in severe respiratory distress          (SpO2 < 93% on RA, but oxygen responsive)

Description of Study Agent/Procedure	
Hyperbaric oxygen therapy involves placing patients in an enclosed chamber with 100% inhaled oxygen at an increased atmospheric pressure. HBOT chambers have shown efficacy and been cleared by the FDA for 13 conditions:
 
 
• Air or gas embolism
 
• Carbon monoxide poisoning
 
• Clostridial myositis and myonecrosis (gas gangrene)
 
• Crush injury, compartment syndrome, and other acute traumatic ischemias
 
• Decompression sickness
 
• Enhancement of healing in conditions including:                     
 
◦ Diabetically derived illness, such as diabetic foot, diabetic retinopathy, diabetic nephropathy
 
◦ Exceptional blood loss (anemia)
 
◦ Intracranial abscess
 
◦ Necrotizing soft tissue infections (necrotizing fasciitis)
 
◦ Osteomyelitis (refractory)
 
◦ Delayed radiation injury (soft tissue and bony necrosis)
 
◦ Skin grafts and flaps (compromised)
 
◦ Thermal burns
 
 
 

Reference Therapy	
Standard of care matched cohort of patients that did not receive HBOT based on age and gender and if possible underlying medical comorbidities and initial disease severity.

Key Procedures	
 
• Hyperbaric Oxygen Treatment
 
• Review of standard of care pre and post treatment blood draws to evaluate the blood oximetry along with markers of inflammation (e.g., D-dimer, Lymphocytes, IL-6, Ferritin, LDH, CRP, ESR, Fibrinogen, and troponin)
 
• Chart review
 

Statistical Analysis	
For binary primary and secondary endpoints, chi-squared analysis of proportions between the two matched groups with multivariate logistic regression if we find identifiable differences in the two study arms. T-test and linear regression for secondary endpoints that are continuous variables.

CONFIDENTIAL

This material is the property of the NYU School of Medicine and Langone Medical Center. Do not disclose or use except as authorized in writing by the study sponsor

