#### **4.2.2 Secondary Study Endpoints**

The secondary endpoints will be whether a patient needed invasive mechanical ventilation and the number of days on a ventilator for those who did receive ventilation. The rate of patients who needed mechanical ventilation among those who received hyperbaric oxygen will be compared to the rate in a matched cohort of patients that received standard of care and did not get hyperbaric oxygen.

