## **7.9 Rescue Medications, Treatments, and Procedures**

While in the chamber the patient will be attended to by an attending physician certified in hyperbaric medicine. Participants in this study are in respiratory distress and at risk for respiratory failure. If the patient develops respiratory failure, rescue therapy would be mechanical ventilation. In the event of a "code" the code team will be called and assume care of the patient upon arrival. Patients will be monitored by direct observation and cardiac monitor if indicated. Patients can be rapidly decompressed and removed from the chamber within 90 seconds if needed.

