### 9.3 Analysis Datasets

We will compare study endpoints and safety outcomes between the 40 patients who received HBOT treatment with a matched comparison group of 120 patients who received standard treatment. Matching will be based on age, gender, comorbidity, and disease severity. The eligibility criteria for the SOC group will be consistent with that of the HBOT group.

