### 9.4 Description of Statistical Methods

#### 9.4.1 General Approach

We will summarize the continuous variables using mean, median, standard deviation and ranges, and the categorical variables using frequency and proportions. Variables will also be summarized graphically. Baseline characteristics of the participants who received HBOT will be compared with that of control patients receiving SOC. If we find any significant difference in the baseline variables between the two matched groups, we will adjust for them as covariates in outcome analysis. T-test or ANOVA will be used for continuous variables whereas chi-squared test will be used for comparison of proportions. All tests will be two tailed at significance level of 0.05. Appropriate transformations (such as log transformation) will be considered for any continuous variable that indicates non-normality. Statistical software R and SAS will be used for the analysis.

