#### 9.4.2 Analysis of the Primary Efficacy Endpoint(s)

The primary endpoint will be patient mortality, a binary outcome variable indicating whether a patient died during hospitalization for COVID treatment. We will compute proportion of patients who died in each

CONFIDENTIAL

This material is the property of the NYU School of Medicine and Langone Medical Center. Do not disclose or use except as authorized in writing by the study sponsor

matched group. Chi-squared test will be utilized to compare rates of incident mortality in each group. We will also report estimates of difference in proportions along with an estimate of uncertainty using 95% confidence interval.

As a follow-up analysis, we will use a multivariable logistic regression, adjusting for any baseline covariates determined to be confounder, to estimate odds-ratio of probability of mortality between HBOT group and SOC group. We will also report 95% confidence interval of the odds-ratio.

Sample size consideration: Using a sample of 160 patients, 40 in HBOT arm and 120 in SOC arm (post matching) we can detect a reduction of 22.5% with 80% power at significance level of 0.05, assuming that the proportion of mechanical ventilation needed in SOC arm is about 80%.

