### **9.5 Sample Size**

Using a sample of 160 patients, 40 in HBOT arm and 120 in SOC arm (post matching) we can detect a reduction of 22.5% or higher, against the null of no difference, with 80% power at significance level of 0.05, assuming that the mortality rate in SOC arm is about 80%.

For the secondary analysis, our proposed sample of 160 patients will similarly allow us to detect a difference of 22.5% in need for ventilation between HBOT group and SOC group with 80% power. For comparing the continuous outcome of number of days in ventilation, we have 80% power to detect effect size (cohen's d) of 0.51 with 160 patients.

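### Treatment-limitation orders at index are not matched on, screened for or collected, so unequal prevalence between HBOT and SOC could bias mortality and ventilation in opposite directions

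*Combined protocol and SAP*

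**What the plan says.** The SOC group is built by chart review, three charts per HBOT patient (section 5.7). The matching factors are described in three ways:

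- The Brief Summary in the Protocol Summary, and section 4.1, name age and gender only.
- The Reference Therapy row of the Protocol Summary has a "matched cohort of patients that did not receive HBOT based on age and gender and if possible underlying medical comorbidities and initial disease severity".
- Section 9.3 drops the qualifier: "Matching will be based on age, gender, comorbidity, and disease severity". It adds that SOC eligibility will be consistent with HBOT eligibility.

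The eligibility criteria (Protocol Summary, sections 5.1 and 5.2) do not mention a do-not-intubate, do-not-resuscitate or comfort-care order. Section 7.1.2 lists what is taken from the record: history, medication, examination, laboratory results and imaging. Order status is not named. Sections 9.4.1 to 9.4.3 adjust for baseline variables that differ between the groups or are judged to be confounders.

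The primary endpoint is death in hospital (section 9.4.2). For ventilation, section 4.2.2 says: "The secondary endpoints will be whether a patient needed invasive mechanical ventilation". Section 7.9 says of HBOT participants: "If the patient develops respiratory failure, rescue therapy would be mechanical ventilation".

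**The concern.** The two groups enter by different routes. An HBOT patient is referred by a physician who expects benefit (section 5.5), consents, and is moved to a chamber with intubation and a code team as back-up (sections 4.1 and 7.9). An SOC chart only has to meet the listed criteria and match. The proportion of patients with a limit on treatment could easily differ between them.

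Such a limit bears directly on both main endpoints. A patient whose do-not-intubate order is followed cannot reach the ventilation endpoint. Death in hospital is plausibly more likely when intubation or resuscitation is withheld. Matching on age, comorbidity and severity may remove part of an imbalance but need not remove all of it, because equally ill patients make different decisions.

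The two biases have opposite signs. An excess of orders in SOC favours HBOT on mortality and disfavours it on ventilation; an excess in HBOT does the reverse. A mortality benefit without a ventilation benefit could therefore arise from this source alone. Without randomisation (section 9.6.1), matching is the main protection against it.

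**Working it through.** **Inputs from the plan.** There are 40 HBOT and 120 SOC patients. On the test: "All tests will be two tailed at significance level of 0.05". On power, section 9.5 claims to "detect a reduction of 22.5% or higher, against the null of no difference, with 80% power at significance level of 0.05". The mortality assumption behind that claim reads: "assuming that the mortality rate in SOC arm is about 80" per cent. Section 9.4.2 has the parallel statement for ventilation, "assuming that the proportion of mechanical ventilation needed in SOC arm is about 80" per cent.

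**The plan's figure first.** Read 22.5% as percentage points, so 80% v 57.5%. The pooled rate is (120 × 0.80 + 40 × 0.575)/160 = 0.744. The null standard error is √(0.744 × 0.256 × (1/120 + 1/40)) = 0.0797, and the alternative standard error is √(0.80 × 0.20/120 + 0.575 × 0.425/40) = 0.0863. Power = Φ((0.225 − 1.96 × 0.0797)/0.0863) = 78.7%. Exact enumeration of the uncorrected chi-squared test gives 79.2%. The stated 80% reproduces, so this point does not depend on a sample-size error.

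**Assumed inputs.** The documents give no prevalence of orders and no outcome rates for patients who have them. Let f be the share of SOC patients with an order in excess of the HBOT share. The scenarios put none in HBOT.

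**Mortality, no true HBOT effect.** False difference = f × (mortality with an order − mortality without). The last column is the exact probability of a significant result favouring HBOT at 40 v 120, first at f = 0 and then at the stated f.

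| Mortality without order | With order | f | SOC rate | False difference | False significant benefit |
|---|---|---|---|---|---|
| 80% (plan's rate) | 95% | 10% | 81.5% | 1.5 points | 3.0% → 4.8% |
| 80% (plan's rate) | 95% | 15% | 82.25% | 2.25 points | 3.0% → 6.0% |
| 80% (plan's rate) | 95% | 20% | 83.0% | 3.0 points | 3.0% → 7.4% |
| 50% | 95% | 20% | 59.0% | 9.0 points | 2.5% → 17.0% |
| 30% | 80% | 15% | 37.5% | 7.5 points | 2.2% → 12.8% |
| 30% | 95% | 20% | 43.0% | 13.0 points | 2.2% → 30.2% |

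The table takes 80% as the rate in patients without an order. If the plan's 80% is instead the overall SOC rate, with f = 15%, the rate without an order is (0.80 − 0.15 × 0.95)/0.85 = 77.4%. The false difference is then 2.6 points and the chance of a false significant benefit is 6.4%.

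**Ventilation, true 22.5-point reduction.** Take 80% as the rate in full-treatment patients, 57.5% under HBOT, and no ventilation in patients with a do-not-intubate order. The observed SOC rate is 0.80 × (1 − f).

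| f | SOC rate | Observed difference | Exact power |
|---|---|---|---|
| 0 | 80% | 22.5 points | 79% |
| 10% | 72% | 14.5 points | 40% |
| 15% | 68% | 10.5 points | 23% |
| 20% | 64% | 6.5 points | 12% |

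**The other direction.** If 15% of HBOT patients and no SOC patients had a do-not-intubate order, the HBOT rate with no true effect would be 0.80 × 0.85 = 68% against 80%. That is a false 12-point ventilation benefit. The mortality bias would then run against HBOT.

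**The case against.** Several objections have force.

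- **Direction.** A reader might infer that SOC must contain more limited-care patients, so that any mortality benefit is suspect. The documents do not support that. The HBOT criteria do not exclude such patients either, and consent through a legally authorised representative is allowed (sections 12.3.1 and 12.4), so consent is not a firm filter. Bias needs unequal prevalence, and the plan is silent on prevalence.
- **Size on mortality.** A reader might infer a large false mortality benefit. That requires mortality in full-treatment patients well below the plan's 80%. An extreme case, with orders in 25% v 0% and mortality of 90% v 20%, gives 17.5 points and a 54% chance of a false significant benefit, but it combines three assumptions far from the plan's rate. At 80% there is little room for deaths to rise. Whether 80% is realistic is a separate question.
- **Adjustment.** A reader might infer that the analysis cannot deal with this because order status is not a matching factor. That is wrong: sections 9.4.1 to 9.4.3 allow adjustment for any baseline variable that differs or confounds. The gap is narrower. Order status is not a listed chart item, and adjustment cannot use a variable that was not abstracted.
- **Partial protection.** Section 9.3 matches on comorbidity and severity without qualification and aligns SOC eligibility with HBOT eligibility. This probably removes some of the imbalance, and the figures above are not reduced for it. However, the Protocol Summary promises those two factors only where possible, and aligned eligibility does not help when the criteria omit the item.
- **One confounder among several.** This is an openly non-randomised pilot cohort, and physician referral selects on more than order status. One extra field does not cure that. It remains worth collecting because it determines whether one of the endpoints can occur at all.

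**Conclusion.** The gap stands, with no direction attached. Order status at index is absent from every matching list, from the eligibility criteria and from the listed chart data, while the two groups enter by routes that make unequal prevalence plausible. Following the plan as written can bias both main endpoints, in opposite directions.

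The consequence is larger for ventilation than for mortality at the plan's own rates. A 15% excess in SOC moves mortality by 2.25 points but lowers power for the planned ventilation effect from 79% to 23%. At an assumed full-treatment mortality of 30%, with 80% in limited patients, the same excess moves mortality by 7.5 points, one third of the 22.5-point target. All prevalences and all outcome rates in limited patients are assumptions, and the documents do not allow the actual bias to be estimated. The change should be made before SOC charts are abstracted.

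**What to change.** Amend section 9.3, the Reference Therapy row and section 7.1.2 as follows.

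1. Define an index time: the first HBOT session for treated patients, and the corresponding time of meeting eligibility for SOC charts.
2. For both groups, abstract whether a do-not-intubate, do-not-resuscitate or comfort-care order was in force at that time, with its date.
3. Match on that status. If matching is not feasible, adjust for it in the logistic and linear models already planned.
4. Analyse the ventilation endpoint in patients with no do-not-intubate order at index, and report the others separately.
5. Do not use orders dated after index for matching or adjustment, because they may result from deterioration.

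The cost is one dated chart field per patient and a somewhat smaller pool of SOC charts. Section 9.6.1 says eligible charts are plentiful, so this should be affordable, although the plan gives no count. Restricting the ventilation comparison may leave fewer than 40 and 120 patients for that endpoint. The change concerns data collection and analysis only, and it does not remove other selection arising from physician referral.

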### Schematic of Study Design

#### ***Intervention arm:***

Cohort A	Treatment arm	40	HBO
----------	---------------	----	-----

#### ***Chart review:***

Cohort A	Treatment arm	40	HBO
Cohort B	SOC	120	SOC

CONFIDENTIAL

This material is the property of the NYU School of Medicine and Langone Medical Center. Do not disclose or use except as authorized in writing by the study sponsor  
Interventional Template Version: 11 January 2019

## 2 Introduction, Background Information and Scientific Rationale

### 2.1 *Background Information and Relevant Literature*

A novel coronavirus, similar to the one that caused severe acute respiratory syndrome (SARS) that began in Wuhan, China, is now a pandemic. With first cases confirmed in the United States nearly 4-6 weeks ago, we anticipate this spread will continue to increase before it plateaus or even decreases. It is highly contagious and is quickly evolving. The first cases were originally linked to animal-human transmission but has since then been transmitted from human-to-human at an exponential rate. Aerosol transmission through respiratory droplets from coughing or sneezing is another primary mechanism.

However, those individuals that are affected have presented in variable clinical presentations from asymptomatic to mild disease to extensive systemic immune reactions requiring mechanical ventilatory assistance. The pathogenic mechanism is still under research but seems complex. The viral infection amounts an excessive immune reaction within the host, activating leukocytes and interleukins that maintain a pro-inflammatory disease state.

Hospital staff, beds, and supplies are limited. The growing number of patients requiring supplemental oxygen and mechanical ventilation is increasing. There is an urgent need to capture this subset of COVID-19 patients prior to clinical respiratory deterioration.

Hyperbaric oxygen therapy (HBOT) presently has been trialed in Wuhan and Italy and has shown feasibility and safety. Hyperbaric oxygen provides patients with 100% inhaled oxygen at an increased atmospheric pressure and has been used as adjuvant therapy to decrease inflammatory states. It has been used in supportive therapy for refractory hypoxia, however, the efficacy of HBOT in treating severe hypoxia in patients with COVID-19 has not been evaluated. Due to the severity of this illness further treatment and studies are needed to begin as soon as possible.

